## 11.2.2 Pre-existing Conditions

For purposes of this Study a pre-existing condition means a diagnose, clinically significant finding, symptom, or laboratory abnormality present at baseline (Visit 1). Subsequently, during the course of the Study it shall be recorded as an AE/SAE if the frequency, intensity, or the character of the condition worsens during the study period.

## 11.2.3 Overdose

All overdoses with or without associated symptoms, should be reported as AEs on the appropriate eCRF page. An overdose is defined as dose exceeding the specified dose for each week. If sequelae meeting the criteria for a SAE have occurred in association with the overdose, the case must be reported immediately, within 24 hours. An assessment whether the overdose was accidental or intentional should be recorded. If the overdose was a suicide attempt, this fact should be clearly stated. The AEs and SAEs that occur as a result of an overdose should be recorded on the eCRF.

## 11.2.4 Pregnancy

Coversin is contraindicated during pregnancy. If pregnancy is suspected, a blood sample for serum HCG examination must be sent to the sub-contracted laboratory within 48 hours. As during the first pregnancy weeks the test may be negative it may be confirmed by an ultrasound examination. Based on the current available knowledge the effects of Coversin on a fetus are unknown therefore the company recommendation is for the patient to be withdrawn from the study or terminate pregnancy, unless in the opinion of the PI, the patient has no other treatment options and is at risk of life-threatening hemolysis if Coversin is discontinued. All pregnancies (even if suspected) must be reported on the appropriate eCRF page (Pregnancy form) within 24 hours from the moment when the investigator became aware of the pregnancy (or suspected pregnancy). In any case each pregnancy must be followed till its termination (either by birth of a child or abortion) and the eCRF Pregnancy form has to be updated.

## **11.3 Reporting Procedures for Serious Adverse Events**

Any SAE occurring during the Study has to be managed by established Standards of Care to protect life and health of participating patients. If such treatment represents a significant deviation from the protocol, the Investigator shall immediately notify the study monitor and/or the Sponsor to determine whether the patient should be dropped out from the Study, or not.

All Serious Adverse Events, irrespective of their causality, must be notified to the Pharmacovigilance provider (PVP) of the Sponsor, **within 24 hours** of Investigator's knowledge of the event. Reporting shall be done on the corresponding SAE form, provided to each center during the initiation visit, and sent by fax or e-mail to:

PVP SAE hotline: [contact] E-mail: [contact]

The provided information shall contain as much details regarding the event as actually available. Investigators shall not wait to receive additional information to fully document the event, before notifying the SAE to Akari Therapeutics Plc. The SAE reporting form should detail all relevant aspects of the AEs listed in Section 11.2.1. Where applicable, information from relevant hospital records or autopsy reports should be obtained and provided to Akari Therapeutics Plc.

## 11.4 Expedited Safety Reporting

Any Serious Adverse Event, which is unexpected and at least possibly related to the IMP, requiring expedited reporting to the respective regulatory authority, EudraVigilance and ECs/ Institutional Review Boards (IRB) of the sites participating in this Study is subject to following timelines:

- 7 calendar days for SUSARs involving death and life-threatening events.
- 15 calendar days for SUSARs involving hospitalization or prolongation of hospitalization or persistent or significant disability/incapacity or congenital anomaly/birth defect or any other significant clinical/laboratory event of major concern in the opinion of the Investigator.

Day zero (clock start) for expedited reporting purposes is the date of initial information or of the relevant follow-up information received in any form (in writing or verbal) by any personnel of Sponsor or contracted parties including the CRO and the PVP.

All SUSARs will be reported to the respective competent authorities, ECs (IRBs) and Investigators within specified timelines in accordance with corresponding national legislation.

## 11.5 Development Safety Update Reports

Development Safety Update Reports will be prepared by Akari Therapeutics Plc, on an annual basis and distributed to all competent authorities and to relevant ECs in accordance with the corresponding national regulations.

## **11.6 Data Safety Monitoring**

A Monitor will be assigned by the Sponsor to ensure the data is source data verified. Additionally, the Sponsor's designated Pharmacovigilance Provider (PharmInvent) will hold the safety database, their primary role will be to notify the Sponsor of any safety issues related to Coversin and perform reconciliation between the clinical and safety database. There will be a monthly review by the

Page 64 of 84 AKARI Confidential Sponsor's Medical Director(s) to review all clinical data as it becomes available with a view to picking up any possible safety signals including laboratory trends that occur within the range of normal. Based on the available data thus far, there are no obvious safety signals or trends, however close monitoring and evaluation will be carried out.

## **12 STATISTICS**

## **12.1 Statistical Methods**

The statistical approach taken will depend on the number of patients recruited.

If less than 4 patients are recruited, each patient will be analyzed separately and no formal statistical analysis plan will be written. Changes in the primary efficacy outcome during the period baseline to mean of Day 43, 60, 90, 120, 150 and 180 will be analyzed using linear regression using all measurements in the analysis. Secondary efficacy outcomes measured multiple times will be analyzed in an equivalent manner.

If 4 or more patients are recruited, the patients will be analyzed as a single group. Differences between specific time points (e.g. baseline and mean of Day 43, 60, 90, 120, 150 and 180) for the primary and secondary efficacy endpoints will be performed using the paired t-test.

Additionally, the change in the primary efficacy outcome over time will also be examined using all measurements. Mixed model will be used to allow for repeat measurements from the same patients, with the patient considered as a random effect.

## **12.2** Number of Patients

A total of up to 6 patients may be enrolled under this Protocol.

## 12.3 Significance Level

All significance tests will be purely descriptive.

## 12.4 Missing, Unused or Spurious Data

Missing data that cannot be retrieved from source records or other repositories will be recorded as such in the eCRFs and will not be entered into the statistical analysis. Spurious data will be examined by the Sponsor's monitor, medical or statistical advisors and a decision made as to how it should be handled. If there is an obvious transcription or data entry error such as a misplaced decimal point in a biochemical parameter this will be discussed with the site or the laboratory and, if all parties agree, it will be corrected and endorsed by both the Investigator and the Sponsor.

Unused data (e.g. superfluous blood pressure recordings or hematological results in addition to those required by the Protocol) will remain part of the source documentation and only be incorporated into the trial documents and analysis if there is reason for them to be (e.g. an unexpected fall in blood pressure that might constitute an AE).

## 12.5 Deviations from the Statistical Analysis Plan

It is not envisaged that there should be any deviations from the SAP. Any unexpected deviations (e.g. a requirement for a trend analysis not foreseen in planning the trial) will be discussed with regulatory agencies and the rationale for such an analysis will be included in the SAP and Final Study Report.

## 12.6 Patients to be Included in the Statistical Analysis

The primary analysis will be intention to treat (ITT) and all patients entered and who sign informed consent will be included. If there is a difference between this population and all dosed patients (e.g. because a patient decides to withdraw after selection but before the first dose has been administered or because of major Protocol violations such as missed doses) a per Protocol (PP) analysis will also be performed.

All patients will be included in the safety analysis whether completing the trial according to the Protocol or not. Analyses of efficacy at various time points will be made for all patients reaching that point.

'End of study' will be defined as last patient, last visit (Day 180).

The final analysis will be performed using data collected up to the end of the study. This data will be presented in a Final Study Report.

All patients in the study will be included in the safety analysis whether completing the trial according to the Protocol or not. The efficacy analysis will include all measurements made whilst the patient(s) correctly followed the trial protocol.

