#### Table 11: Schedule of Events

The superscript lettering and numbering (pertaining to the table footnotes) have been changed for formatting purposes to ensure the superscripts within the table body are numbers and the superscripts within the table headers are letters.

"Including LDH" has been added to the "Chemistry" procedure row to ensure it is consistent with the rest of the table.

The dose volume has been added to each of the study day headers to provide clarification as to when each procedure and evaluation should be performed.

CH50 analyses have been added on Days 29, 36, 43, 60, 90, 120, 150, 180 and 120, as these were inadvertently not included in the previous amendment.

Hematology analyses have been added on Days 29, 36, 43, 60, 90, 120, 150 and 180, as these were inadvertently not included in the previous amendment.

Coversin level (PK), Total C5, ADA, LTB4, chemistry, hematology and a urine pregnancy test have been added to Day 210, to ensure the full safety profile of the patients can be obtained during this safety follow up visit.

The 'Patient Self-Administration Questionnaire' has been removed from Day 1 (baseline), Day 7 and Day 14 (pre-dose 22.5mg dose), to ensure it is consistent with the body of the protocol.

'Initiation Phase' and 'Maintenance Phase' have been added to the headers of the Schedule of Events tables, to ensure that they reflect what is written within the Protocol body and aims to assist the Investigators in determining which phase the patients are in.

The abbreviation for "Hours" has been changed to "Hrs" throughout the table to ensure it is consistent with the rest of the protocol.

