# **1 PROTOCOL SYNOPSIS**

Protocol Title:	CONSENT II: Coversin in Paroxysmal N octurnal Hemoglobinuria (PNH) in patients with resistance to E culizumab due to complement C5 Polymorphisms		
Protocol Number:	AK585		
Sponsor:	Akari Therapeutics Plc. [name]		
Investigational Product(s):	Coversin (rVA576) powder for solution for subcutaneous injection 30 mg/mL		
Phase of Development:	II Indication: Paroxysmal nocturnal hemoglobinuria (PNH)		
Study Centre(s):	Up to 6 centers		
Objectives:	
 
Primary Objective: Safety of Coversin (rVA576)
 
Secondary Objective: Efficacy of Coversin in the treatment of patients with PNH resistant to eculizumab (Soliris®)
 
		
Study Design:	Phase II Open-label, single arm		
Planned Number of Subjects:	Up to 6		
Subject Population:	Patients with PNH, male or female, with proven resistance to eculizumab (Soliris ® ) due to complement C5 polymorphisms		
Criteria for Inclusion and Exclusion:	
 
Inclusion Criteria:
 
1. Patients with known paroxysmal nocturnal hemoglobinuria (PNH).
 
2. Aged 18 and above. No upper age limit.
 
3. LDH ≥1.5 ULN.
 
		

4.	Patients must agree to avoid pregnancy and fathering children from
	the time of screening through the end of safety follow-up. Permitted
	contraceptive methods that are ≥99% effective in preventing
	pregnancy should be communicated to trial subjects and their
	understanding confirmed.
5.	Resistance to eculizumab (Soliris ® ) proven by either a recognized
	C5 polymorphism on genetic screening or complement inhibition
	on CH50 ELISA of <100% at concentrations of eculizumab
	(Soliris ® ) in excess of 50µg/mL. Genetic conformation of the
	polymorphism should be obtained on all patients as soon as
	practicable but absence of such confirmation will not exclude a
	patient from starting treatment.
6.	The patient has given voluntary written informed consent.
7.	Willing to self-inject Coversin daily.
8.	Willing to receive appropriate prophylaxis against Neisseria
	infection by both immunization and continuous or intermittent
	antibiotics.
9.	Willing to avoid prohibited medications for duration of study
	tizanidine (if on ciprofloxacin) and eculizumab (Soliris®) should be
	discontinued before Coversin therapy is commenced. Ideally this
	should be 2 or more weeks before commencing Coversin unless, in

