## 3.2 Endpoints

Primary Efficacy Endpoint:

• Reduction in serum LDH from baseline to mean of Day 43, 60, 90, 120, 150 and 180

Secondary Efficacy Endpoints:

- Change in LDH from baseline at monthly intervals after Day 28, 60, 90, 120, 150 and 180
- Change in mean Hb: baseline Day 180
- Change in FACIT score: baseline Day 28 Day 180
- Change in EQ-5D-5L QLQ C30 score: baseline Day 28 Day 180
- Number of transfusions: baseline to Day 180

Safety Endpoints:

- Frequency, type and relationship of AEs and SAEs to treatment
- Out of range laboratory parameters (hematology and chemistry)
- Vital signs (blood pressure, body temperature and pulse rate)
- ECG abnormalities baseline Day 180 (A resting pre-dose ECG taken within 7 days of first dose will be compared with ECGs taken 1- 6 hours post-dose and at 180 days of treatment with Coversin)
- Change in weight will be noted baseline and at Day 180
- Injection site reaction and lymph node inspection
- Anti-Coversin antibody production

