## Follow Up Visit – Day 210 (+5 days)

At Day 210 (+5 days), a follow up visit will occur to ensure all outstanding or new AEs are addressed. Patients entering the long-term safety trial are excluded from the follow up visit.

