## Entering the Long-Term Safety Trial

After 180 days, the patient may enter the long-term safety trial or begin an alternative treatment.

The decision to continue on Coversin after the 180 day treatment period should be made by the patient in consultation with the Investigator at or about the 150 day time point. This allows alternative treatment logistics to be arranged if the patient prefers alternative therapy after study completion.

If the patient and Investigator are satisfied with Coversin treatment the patient may enroll onto the long-term safety trial at Day 181. Coversin will be provided through this mechanism until it is approved and locally reimbursed.

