Procedures	Pre- 45mg dose	Pre- 45mg dose	3hrs Post- 45mg dose	6hrs Post- 45mg dose	9hrs Post- 45mg dose	12hrs Post- 45mg dose	18hrs Post- 45mg dose	24hrs Pre- 45mg dose c	Pre- 45mg dose	Pre- 45mg dose	Pre- 45mg dose	Pre- 45mg dose	Pre- 45mg dose	Pre- 45mg dose	Day 210 (+5 days) e
Eligibility, ICF & Medical History										X 7					
Physical Examination 1	х	х								х	х	x	х	х	х
Nasal & Throat Swabs 															
Vital Signs  (including height & weight)	x	х						х		х	х	х	х	х	х
ECG 											х	х	х	х	
CH50	х	х	х	х	х	х	х	х	х	х	х	х	х	х	х
Coversin Drug Level (PK)	х	х	х	х	х	х	х	х	х	х	х	х	х	х	х
Total C5	х	х	х	х	х	х	х	х		х	х	х	х	х	х
Antibodies (ADA)	x	х								х		x		х	х
LTB4	х	х							х	х		х		х	х
LDH Isoenzymes											х			х	
FLAER														х	
Meningitis prophylaxis 5								As per s	ite schedule	-					
Chemistry	x	х							х	х	х	x	х	х	х
Hematology	х	х							х	х	х	x	х	х	х
Urinalysis	x	х								х	х	x	x	х	х
Pregnancy Test Monthly 	х									х	х	x	х	Serum	х
Questionnaire on Self Injection	x										х			Х	
EQ-5D-5L & FACIT	х	х							х	х	х	х	х	Х	
Drug Accountability	х	х							х	х	х	х	х	Х	
IMP administration (±1hr)	х	х				х		х	х	х	х	х	х	Х	
AEs & Concomitant Medications	х	х	х	х		х	х	х	х	х	х	x	x	х	х

a These samples are to be taken 12hrs after the first dose in the morning and pre-second dose of Coversin

b These samples are to be taken 18hrs post dose referring to the first Coversin dose given the morning before

° This sample is to be taken 24hrs after the last Coversin dose and prior to the next 24-hourly dose

d Day 150 – Investigator and patient to confirm if patient will continue onto the long-term safety trial or begin alternative treatment. At Day 181, the patient will enter the long-term safety trial on Coversin or begin alternative treatment and not enter the long-term safety trial.

e Safety follow up visit is not required if the patient is entering the long-term safety and efficacy trial

-  Physical Examination Inclusive of vein assessment and injection site inspection.

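### Safety is the primary objective, but the final-analysis data stop at the last patient's Day 180, before the Day 210 safety visit if that patient does not roll over; separately, the causality terms leave at least one type of event without a term

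*Combined protocol and SAP*

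**What the plan says.** The synopsis gives "Primary Objective: Safety of Coversin (rVA576"). Section 12.6 says that the end of study "will be defined as last patient, last visit (Day 180"), and then: "The final analysis will be performed using data collected up to the end of the study".

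Section 5.2 adds a later contact. At Day 210 (+5 days) "a follow up visit will occur to ensure all outstanding or new AEs are addressed". Table 11, footnote e, limits who attends: "Safety follow up visit is not required if the patient is entering the long-term safety and efficacy trial". Rolling over is optional, because after 180 days "the patient may enter the long-term safety trial or begin an alternative treatment". The Amendment 2 summary explains why laboratory tests were added at Day 210: "to ensure the full safety profile of the patients can be obtained during this safety follow up visit". For patients who stop early, Sections 5.3 and 6.3 require 30 days of follow-up (a minimum in Section 5.3).

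Section 3.2 lists "Anti-Coversin antibody production" and the relationship of adverse events to treatment among the safety endpoints. Section 11.2.1 offers three causality terms:

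- *Unrelated*: the timing does not fit and another cause could account for the event, or the event is beyond dispute not due to the drug.
- *Possible related*: the timing fits and another cause is unlikely.
- *Related*: the timing fits and nothing else can account for the event.

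Section 11.4 applies expedited reporting to unexpected serious events rated possibly related or higher.

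**The concern.** For a completer who does not roll over, the last visit is Day 210, so the definition in Section 12.6 disagrees with the schedule. Followed literally, the analysis of the primary objective closes before a visit that exists only for safety. Table 11 still marks study drug at Day 180, so Day 210 is that patient's only scheduled visit after the last dose. It also carries the only antibody sample scheduled after the last dose.

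Section 12.1 foresees no formal SAP if fewer than 4 patients are recruited. Section 12.6 could then be the only text that fixes the cut.

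The causality wording is a separate matter that bears on the same safety analysis. If an event meets no definition, the investigator must pick a term that does not fit. That choice feeds both a listed safety endpoint and the expedited-reporting rule. Worsening of a pre-existing condition must be recorded as an adverse event (Section 11.2.2), so events that PNH could explain are to be expected.

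**Working it through.** **Data cut.** The plan states no figure for the gap, so there is none to reproduce. Inputs: Day 180 visit ±3 days (Table 11); Day 210 visit, 0 to +5 days (Section 5.2, Table 11); 30 days of follow-up after stopping (Sections 5.3 and 6.3); at most 6 patients (Section 12.2).

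1. Last patient does not roll over, nominal Day 180: 210 − 180 = 30 days to 215 − 180 = 35 days after the cut.
2. With the Day 180 window: 210 − 183 = 27 days to 215 − 177 = 38 days.
3. Another non-rollover patient, first dosed s days before the last patient: on the last patient's calendar the visit falls on Day 210 + a − s (a from 0 to 5) and the cut on Day 180 + b (b from −3 to +3). The visit misses the cut when s < 30 + a − b. The right-hand side runs from 30 + 0 − 3 = 27 to 30 + 5 + 3 = 38. Below 27 days the visit is always missed, from 38 days it is always kept, and in between it depends on the actual dates.
4. A patient who stops treatment w days before the cut, with w under 30, has 30 − w days of required follow-up after it, so up to 30 days.
5. Content of the visit: Table 11 marks 12 rows at Day 210 (physical examination, vital signs, CH50, drug level, total C5, ADA, LTB4, chemistry, hematology, urinalysis, pregnancy test, AEs with concomitant medications). Without the pregnancy test, it is 11 for men.
6. ADA samples: baseline and Days 7, 14, 21, 29, 36, 60, 120, 180 and 210, which makes 10. One of them, Day 210, follows the last dose.
7. One affected patient is at least 1/6 of the trial. The documents give no rollover or accrual rate, so no expected number of affected visits can be derived.

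**Causality.** Cross timing (2 levels) with the alternative cause (3 levels) and apply the three definitions:

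| Timing | Another cause could well explain | Another cause unlikely | No other cause can explain |
|---|---|---|---|
| Compatible | no term | *Possible related* | *Related* |
| Incompatible | *Unrelated* | no term, or *Unrelated* | no term, or *Unrelated* |

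The count of empty cells depends on the reading:

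- Cause levels taken as exclusive, and the beyond-dispute clause in *Unrelated* not met: 3 of 6 empty.
- The same, except that an unlikely cause still counts as one that could explain the event: 2 of 6.
- Incompatible timing accepted as settling that the drug is not the cause: 1 of 6.

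The cell with compatible timing and a credible other cause is empty on every reading, unless the event is itself beyond dispute unrelated.

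**The case against.** On the data cut, the sponsor can say that last visit is the operative phrase and Day 180 a loose gloss, since a non-rollover patient's last visit is Day 210. The loss is also contingent: with at most 6 patients it may never occur. All significance tests are descriptive (Section 12.3), so no test is made wrong. The contingency and the absence of an inferential error both stand. The gloss argument does not remove the problem, because it concedes that the sentence fixing the cut has two readings. The statement in Section 12.6 that all patients enter the safety analysis settles who is included, not up to when.

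A reader might infer that Day 210 data are never analyzed, or that events after Day 180 go unrecorded. The documents support neither. The cut is one calendar date, so earlier patients' Day 210 visits are included. Table 11 schedules AE collection at Day 210, and serious events are notified within 24 hours whatever their cause (Section 11.3). Nor is Day 210 necessarily an untreated observation, since the patient may have begun another therapy.

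On causality, a reader might infer that three combinations certainly lack a term. That is too strong. The beyond-dispute clause can absorb both incompatible-timing cells. It does so most naturally for events before the first dose, which are recorded because collection starts at consent. The Sponsor may also judge causality itself (Section 11.1.2), and medical review is monthly (Section 11.6). These safeguards limit the harm but do not supply the missing term.

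**Conclusion.** The concern holds in a limited form. Section 12.6 conflicts with the schedule for any last patient who does not roll over. That patient's only scheduled safety visit after Coversin then falls 30 to 35 days after the cut (27 to 38 with the window). Other non-rollover patients first dosed less than 27 to 38 days before the last patient, and patients still in the 30-day follow-up after withdrawal, can be affected in the same way. If the last patient rolls over and no other follow-up is pending, nothing is lost. This assumes that the cut is applied literally as Day 180.

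The causality terms are not exhaustive: at least 1, and up to 3, of 6 combinations have no term. Only the well-timed event with a credible other explanation is a certain gap. The number of misclassified events cannot be derived from the documents.

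Two further inconsistencies are minor. Section 11.2.1 ends AE recording at premature withdrawal, while Sections 5.3 and 6.3 require 30 days of follow-up. Other provisions cover unresolved events, severe events causing withdrawal, and related events. Section 2.5 proposes not to report Grade 1 injection site reactions, while Section 11.2.1 records all AEs and Section 3.2 makes these reactions an endpoint. Scheduled injection-site inspection covers part of this.

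**What to change.** In Section 12.6, define the end of study and the data cut as the last patient's last safety contact: Day 210 (+5) for patients who do not roll over, or the end of the 30-day follow-up after withdrawal. Include AEs recorded through that contact. The final analysis is then at most about 38 days later, and no later if the last patient rolls over and no other follow-up is pending. No visit or sample is added, because both follow-ups are already required.

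In Section 11.2.1, revise the definitions so that every event fits exactly one term, including the well-timed event that PNH or another drug could well explain. State the cost of the choice. Placing that event in *Possible related* increases the number of events that meet the causality condition for expedited reporting in Section 11.4, and makes the relationship endpoint less discriminating, since most events on daily treatment have compatible timing. Placing it in *Unrelated* does the reverse.

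As minor edits, reconcile the recording window in Section 11.2.1 with Sections 5.3 and 6.3, and Section 2.5 with Sections 11.2.1 and 3.2. State whether Grade 1 injection site reactions go into the eCRF, and remove the overlap of pain and swelling between Grades 1 and 2.

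### Section 12.6 makes ITT the primary analysis, then limits the efficacy analysis to on-protocol measurements, so LDH values collected after missed doses can be dropped

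*Combined protocol and SAP*

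**What the plan says.** Section 12.6 opens its rules on populations with: "The primary analysis will be intention to treat (ITT) and all patients entered and who sign informed consent will be included". It provides for a second analysis when that population differs from all dosed patients, for instance "because of major Protocol violations such as missed doses) a per Protocol (PP) analysis will also be performed". It adds a time-point rule: "Analyses of efficacy at various time points will be made for all patients reaching that point". After stating that safety covers everyone, however they completed the trial, it closes with: "The efficacy analysis will include all measurements made whilst the patient(s) correctly followed the trial protocol".

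Three other sections bear on the point:

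- **Section 12.1.** With four or more patients, comparisons between time points "for the primary and secondary efficacy endpoints will be performed using the paired t-test", and a mixed model on all measurements is added. With fewer than four, "each patient will be analyzed separately and no formal statistical analysis plan will be written", and the primary outcome is examined by linear regression, again on all measurements.
- **Section 12.4.** Missing data that cannot be recovered "will be recorded as such in the eCRFs and will not be entered into the statistical analysis".
- **Section 12.3.** "All significance tests will be purely descriptive".

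The primary efficacy endpoint (Section 3.2) is the reduction in LDH from baseline to the mean of Days 43, 60, 90, 120, 150 and 180.

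**The concern.** The closing sentence of Section 12.6 is a per-protocol data rule applied to efficacy in general. An analyst who follows it removes values that the ITT statement and Section 12.1 would keep. Two analysts could therefore report different primary LDH results from the same patients, each with support in the text.

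The values at risk are not a random subset. Section 6.1 keeps a patient with unsatisfactory compliance on study after retraining and re-ablation, and it asks the Investigator to consider missed doses as a reason for a rise in LDH. LDH measured after missed doses is therefore collected and is likely to be higher than the patient's other values. Dropping it makes the reduction look larger. With at most six patients, one patient's values are visible in the group figure.

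**Working it through.** **Texts side by side.** On LDH collected after missed doses in a patient still on study:

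| Place | Effect on that value |
|---|---|
| 12.6, ITT sentence | patient included; no value excluded |
| 12.6, PP sentence | missed doses lead to an additional PP analysis |
| 12.6, last sentence | value excluded if the protocol was not correctly followed |
| 12.1, regression (fewer than 4) and mixed model (4 or more) | all measurements used |

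The third row cannot be reconciled with the other three unless it is confined to PP.

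**Size.** The plan gives no effect size, SD or power figure, so there is nothing to reproduce. What follows is an illustration.

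Inputs:

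- Six patients, the maximum in Section 12.2.
- Reduction expressed as a percentage of baseline (assumed; Section 3.2 does not fix the scale).
- A 50% fall in all patients when controlled (assumed; Section 6.2 describes a typical fall to half or less of the pre-treatment level).
- LDH at an affected visit 0.8 x ULN above nadir (assumed; this is the single-rise threshold in Section 6.1).
- Baseline B of 1.5 x ULN (the entry minimum, Section 4.1), 3 or 5 x ULN (the last two assumed).

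Formulas:

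- Loss of reduction at an affected visit: d = 100 x 0.8 / B points.
- Patient's mean over six visits with m affected: 50 - m x d/6. If the m values are discarded, the mean is 50.
- Overstatement of the group mean: m x d/(6 x 6) = m x d/36.

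| B (x ULN) | d | Patient mean, m = 1 | Group overstatement, m = 1 | Group overstatement, m = 2 |
|---|---|---|---|---|
| 1.5 | 53.3 | 50 - 8.9 = 41.1% | 1.48 | 2.96 |
| 3 | 26.7 | 50 - 4.4 = 45.6% | 0.74 | 1.48 |
| 5 | 16.0 | 50 - 2.7 = 47.3% | 0.44 | 0.89 |

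One affected visit is the natural case. Endpoint visits are 17 days (43 to 60) or 30 days apart, and Section 6.1 reassesses the patient 1 to 2 weeks after retraining. Two affected visits would need a prolonged or repeated episode.

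Below four patients there is no group mean. The patient's own six-visit mean is then overstated by d/6: 8.9, 4.4 or 2.7 points for one discarded visit.

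**Secondary gap: incomplete six-visit means.** A patient withdrawn before Day 43 has none of the six visits and so no paired difference. One withdrawn three weeks after reverting at Day 60, 90, 120 or 150 (that is, at Day 81, 111, 141 or 171) has 2, 3, 4 or 5 of them. Sections 12.4 and 12.6 imply a mean of the available visits, but do not say so. Section 6.1 requires last-visit assessments at withdrawal, and nothing states whether that LDH enters the mean.

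Example with B = 3, control lost at Day 60 and LDH unchanged at withdrawal. The visit reductions are 50% and 50 - 26.7 = 23.3%.

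- Available visits: (50 + 23.3)/2 = 36.7%.
- With the early-termination value added: (50 + 2 x 23.3)/3 = 32.2%.
- With that value used for all remaining visits: (50 + 5 x 23.3)/6 = 27.8%.

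**The case against.** The closing sentence could be meant as inclusive, or loosely as a description of the PP set. The sentence before it tells against the inclusive reading: safety covers everyone regardless of adherence, so efficacy appears meant to be narrower. If PP was meant, the text needs to say so. It is also open whether a patient who has been retrained and re-ablated counts as following the protocol again, so dropping the values is one reading, though a natural one. Where four or more patients enroll, a SAP is implied (Sections 12.5 and 13) and could settle the handling, but it would have to overrule the protocol's own sentence.

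A reader might infer more than the documents support:

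- **That this sentence is the only rule when fewer than four patients enroll.** It is not. Section 12.1 still prescribes regression on all measurements, and Section 12.4 and the time-point rule in 12.6 still apply.
- **That LDH after loss of control or after reversion is dropped.** Reversion to 12-hourly dosing is specified in the protocol, so the sentence does not remove values taken after it.
- **That the six-visit mean is undefined for every patient withdrawn for inadequate response.** That is true only before Day 43, and Section 5.3 calls inadequate response in the Initiation Phase highly unlikely. Later the mean is unspecified.
- **That withdrawals bias the result by a known amount.** Counting one early failure as 0% among six would give (5 x 50 + 0)/6 = 41.7% instead of 50%. That compares against LDH that is never collected, so it shows sensitivity to how failures are counted, not bias from this sentence.

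**Conclusion.** The contradiction in Section 12.6, and between it and Section 12.1, is on the page and is wrong as written. Its direct effect is that LDH collected after missed doses can be excluded, which would tend to overstate the LDH reduction.

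Under the stated assumptions the effect is modest: 0.4 to 1.5 points on a six-patient mean for one discarded visit in one patient, and 0.9 to 3.0 for two. The direction rests on LDH being higher after missed doses. The size rests on the assumed 50% fall, the 0.8 x ULN rise and the baseline.

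Significance tests are descriptive, and the synopsis lists efficacy as the secondary objective, so a descriptive estimate is at stake and not a formal decision. The handling of incomplete means is missing detail that deserves a sentence, but the point does not depend on it.

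**What to change.** 1. In Section 12.6, confine the closing sentence to the PP analysis.
2. Base the main efficacy analysis on all dosed patients with all collected Day 43 to 180 LDH values, including those after missed doses or other deviations. List any consented but undosed patient separately, since such a patient has no on-treatment LDH.
3. Report treatment failures as n of all dosed patients, whether or not replaced (Section 6.3 leaves replacement to case-by-case decision), with each patient's LDH course.
4. State how the mean is formed from fewer than six visits and whether the early-termination LDH counts. Show one sensitivity analysis for withdrawn patients, for example that LDH used for the remaining visits. This is one option among several.
5. Reconcile the withdrawal wording, because it determines who lacks a full primary value. Sections 5.2, 6.2 and 6.3 speak of considering, discussing or permitting withdrawal. Table 10 in Section 5.3 and the three-week rule in Section 6.1 state it outright.

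The cost is a wording change, some extra analysis and possibly a less favorable LDH figure. No new visits or samples are needed.
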